4.2 Treatment Administration

4.2.1 Pembrolizumab Induction

All patients will receive 3 cycles of pembrolizumab starting cycle 1 day 1. Pembrolizumab should be administered on Day 1 of each 21-day cycle after all procedures/assessments have been completed as detailed on the Study Procedures Table (Section 5.0). Pembrolizumab may be administered up to 3 days before or after the scheduled Day 1 of each cycle due to administrative reasons. All trial treatments will be administered on an outpatient basis. This treatment will be followed by an investigational PET/CT (PET#2), 3 weeks after completion of cycle 3 (+/- 3 days).

Pembrolizumab 200 mg will be administered as an approximately 30 minute IV infusion on day 1 of each 21-day cycle. Sites should make every effort to target infusion timing to be as close to 30 minutes as possible. However, given the variability of infusion pumps from site to site, a window of -5 minutes and +10 minutes is permitted (i.e., infusion time is 30 minutes: -5 min/+10 min). The Pharmacy Manual contains specific instructions for the preparation of the pembrolizumab infusion fluid and administration of infusion solution.

Patients will receive pre-treatment acetaminophen 650 mg po and diphenhydramine 50 mg po given 30 minutes prior to the pembrolizumab infusion. Pembrolizumab 200 mg IV in 50 mL of 0.9% NaCl will be infused over 30 minutes on day 1 of each 21 day cycle.

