4.2.2.2.2 For those with a positive PET #3 (Deauville 4.5)

PET- Adapted Treatment for patients <60 with positive

Patients age <60 with Deauville score of 4-5 on PET#3 may transition to escBEACOPP (escalated bleomycin, etoposide, doxorubicin, cyclophosphamide, vincristine) +/radiation therapy (RT) at the investigators' discretion

- a. Patients with stage I/II disease may transition to 2 cycles of escBEACOPP +/- RT
- b. Patients with stage III/IV disease may transition to 4 cycles of escBEACOPP +/- RT

24

Initial Version date: March 10th, 2017

Amendment 6: March 29th, 2019

c. Patients with progressive/relapsed disease as defined in section 6.1.2.1 will be taken off study.

Patients 60 or older with a Deauville score of 4, 5 positive PET #3 will continue on AVD for a total of four- six cycles of AVD, depending on stage and tolerability.

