4.3.1 Pembrolizumab Dose Modifications

Adverse events (both non-serious and serious) associated with pembrolizumab exposure may represent an immunologic etiology. These adverse events may occur shortly after the first dose or several months after the last dose of treatment. Pembrolizumab must be withheld for drug-related toxicities and severe or life-threatening AEs as per table 4.1 below. See Section 4.5.3 for supportive care guidelines, including use of corticosteroids.

Initial Version date: March 10th, 2017

Amendment 6: March 20th, 2010

Amendment 6: March 29th, 2019

Table 4.1: Dose Modification Guidelines for Pembrolizumab-Related Adverse Events

General instructions:

- Corticosteroid taper should be initiated upon AE improving to Grade 1 or less and continue to taper over at least 4
 weeks.
- 2. For situations where pembrolizumab has been withheld, pembrolizumab can be resumed after AE has been reduced to Grade 1 or 0 and corticosteroid has been tapered. Pembrolizumab should be permanently discontinued if AE does not resolve within 12 weeks of last dose or corticosteroids cannot be reduced to ≤10 mg prednisone or equivalent per day within 12 weeks.
- 3. For severe and life-threatening irAEs, IV corticosteroid should be initiated first followed by oral steroid. Other immunosuppressive treatment should be initiated if irAEs cannot be controlled by corticosteroids.
- 4. For signs or symptoms of Stevens-Johnson Syndrome (SJS) or Toxic Epidermal Necrolysis (TEN), withhold pembrolizumab and refer the patient for specialized care for assessment and treatment.

pembrolizumab and refer the patient for specialized care for assessment and treatment.				
Immune-related AEs	Toxicity grade or conditions (CTCAEv4.03)	Action taken to pembro	irAE management with corticosteroid and/or other therapies	Monitor and follow-up
Pneumonitis	Grade 3 or 4, or recurrent Grade 2	Withhold Permanently discontinue	Administer corticosteroids (initial dose of 1-2 mg/kg prednisone or equivalent) followed by taper	Monitor participants for signs and symptoms of pneumonitis Evaluate participants with suspected pneumonitis with radiographic imaging and initiate corticosteroid treatment Add prophylactic antibiotics for opportunistic infections

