- For Grade 3 or 4 diarrhea/colitis, treat with intravenous steroids followed by high dose oral steroids.
- When symptoms improve to Grade 1 or less, steroid taper should be started and continued over no less than 4 weeks.

Type 1 diabetes mellitus (if new onset, including diabetic ketoacidosis [DKA]) or ≥ Grade 3 Hyperglycemia, if associated with ketosis (ketonuria) or metabolic acidosis (DKA)

- For T1DM or Grade 3-4 Hyperglycemia
 - Insulin replacement therapy is recommended for Type I diabetes mellitus and for Grade 3-4 hyperglycemia associated with metabolic acidosis or ketonuria.
 - Evaluate patients with serum glucose and a metabolic panel, urine ketones, glycosylated hemoglobin, and C-peptide.

Hypophysitis:

- For Grade 2 events, treat with corticosteroids. When symptoms improve to Grade 1 or less, steroid taper should be started and continued over no less than 4 weeks. Replacement of appropriate hormones may be required as the steroid dose is tapered.
- For **Grade 3-4** events, treat with an initial dose of IV corticosteroids followed by oral corticosteroids. When symptoms improve to Grade 1 or less, steroid taper should be started and continued over no less than 4 weeks. Replacement of appropriate hormones may be required as the steroid dose is tapered.

Hyperthyroidism or Hypothyroidism:

Thyroid disorders can occur at any time during treatment. Monitor patients for changes in thyroid function (at the start of treatment, periodically during treatment, and as indicated based on clinical evaluation) and for clinical signs and symptoms of thyroid disorders.

- Grade 2 hyperthyroidism events (and Grade 2-4 hypothyroidism):
 - In hyperthyroidism, non-selective beta-blockers (e.g. propranolol) are suggested as initial therapy.
 - In hypothyroidism, thyroid hormone replacement therapy, with levothyroxine or liothyroinine, is indicated per standard of care.
- **Grade 3-4** hyperthyroidism, treat with an initial dose of IV corticosteroid followed by oral corticosteroids. When symptoms improve to Grade 1 or less, steroid taper should be started and continued over no less than 4 weeks. Replacement of appropriate hormones may be required as the steroid dose is tapered.

Hepatic:

- For **Grade 2** events, monitor liver function tests more frequently until returned to baseline values (consider weekly).
 - Treat with IV or oral corticosteroids
- For Grade 3-4 events, treat with intravenous corticosteroids for 24 to 48 hours.

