5.0 STUDY PROCEDURES

Trial Period:	Screening Phase	Treatment Cycles ¹							Off Rx	Surveillance		
		Pemb	orolizun	nab		AVD ^{2,3}		AVD ^{3,4}	Assessment	Pembrolizumab ⁵	Discont	Survival Follow-Up
Treatment Cycle/Title:	Main Study Screening	1	2	3	PET #2	1-2	PET #3	3-66	emo Asses	4-35		
Scheduling Window (Days):	Within 28 days of registration	1 ± 3	22 ± 3	43 ± 3		64 ± 3		120 ± 3	Post-Chemo	2-4 weeks after last dose of chemotherapy ± 3	30 days after last dose (pembro or AVD, ±5 days)	Every 12 weeks
Administrative Procedures												
Informed Consent	X											
Inclusion/Exclusion Criteria	X											
Demographics and Medical History	x											
Prior and Concomitant Medication Review	х	X	х	x		х		Х		X	X	
Trial Treatment Administration		X	X	X		X		X		X		
Post-study anticancer therapy status											X	X
Survival Status ⁷												X
Clinical Procedures/Assessments												
Review Adverse Events		X	X	X		X		X		X	X^{20}	X^{20}
Physical Examination	X	X	X	X		X		X		X	X	
Vital Signs ⁸ Weight and Height ²⁴	X	X	X	X		X		X		X	X	
ECOG Status ⁹	X	X	X	X		X		X		X	X	
Echocardiogram/MUGA	X							X^{21}				
Unfavorable risk factors/IPS ¹⁰	X											
Laboratory Procedures/Assessments: analysis performed by LOCAL laboratory												
Pregnancy Test – Urine or Serum β-HCG	x ²²	x ²²										
PT/INR and aPTT	Х											

Trial Period:	Screening Phase	Treatment Cycles ¹							Off Rx	Surveillance		
		Pemb	orolizun	nab		AVD ^{2,3}		AVD ^{3,4}	Assessment	Pembrolizumab ⁵	Discont	Survival Follow-Up
Treatment Cycle/Title:	Main Study Screening	1	2	3	PET #2	1-2	PET #3	3-6 ⁶		4-35		
Scheduling Window (Days):	Within 28 days of registration	1 ± 3	22 ± 3	43 ± 3		64 ± 3		120 ± 3	Post-Chemo	2-4 weeks after last dose of chemotherapy ± 3	30 days after last dose (pembro or AVD, ±5 days)	Every 12 weeks
CBC with ANC ¹¹	x ¹¹	X	X	X		x^3		\mathbf{x}^3		X	X	
Comprehensive Serum Chemistry Panel ¹¹	x ¹¹	X	Х	х		x^3		x^3		х	X	
Urinalysis	X											
T3, FT4 and TSH ¹²	X			Х						X		
ESR	X											
HIV, Hepatitis B, Hepatitis C ¹³	X											
Quantiferon-gold TB blood test ²⁵	x ²⁵											
Efficacy Measurements												
PET-CT ¹⁴	x ¹⁴				x ¹⁴		x ¹⁴		X ¹⁵	x ¹⁶	x ¹⁵	
CT scan ¹⁷	X									x ²³	X	
Tumor Biopsies/Archival Tissue Collection/Correlative Studies Blood performed by CENTRAL laboratory												
Archival or Newly Obtained Tissue Collection ¹⁸	X		x ¹⁸									
Correlative Studies Blood Collection ¹⁹		х				х					x	

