⁵ Elderly patients may receive consolidation for a total of up to 1 or 2 years pembrolizumab treatment. Elderly patients who do not achieve CR after additional AVD will have pembrolizumab consolidation for up to 32 additional doses. Elderly patients with Stage III/IV disease who achieve CR after <6 cycles AVD will receive pembrolizumab consolidation for up to 14 additional doses. See section 4.2.3 for details.

⁶ See study schema in 1.2

⁷ Patients will be followed (either by routine clinic visit or by phone call) for survival every 12 weeks (±7 days) for 2 years from the last dose of study drug. Patients should also be monitored for occurrence of an allogeneic stem cell transplant within 24 months from the last study treatment. If patient undergoes an allo-SCT in this timeframe, transplant parameters and adverse events must be reported as specified in section 4.6.3 (up to 18 months from the time of SCT).

⁸ Vital Signs include: Blood pressure, pulse, respiratory rate, and oxygen saturation

⁹ See Appendix A

¹⁰ See Appendix D

¹¹ Comprehensive chemistry panel and CBC with differential are required within 14 days of study registration. Chemistry panel will include glucose, calcium, albumin, ALT, AST, sodium, potassium, total bilirubin, alk phose, and creatinine. CBC with differential must include Absolute Neutrophil Count.

¹² At baseline and every 6 weeks while on therapy with pembrolizumab.

¹³Patients must have HIV Ab screen; and Hepatitis B Sag, Sab, and core; and Hepatitis C Ab testing within 6 weeks of registration.

Trial Period:	Screening Phase	Treatment Cycles ¹						Off Rx	Surveillance			
		Pemb	orolizun	nab		AVD ^{2,3}		AVD ^{3,4}	sment	Pembrolizumab ⁵	Discont	Survival Follow-Up
Treatment Cycle/Title:	Main Study Screening	1	2	3	PET #2	1-2	PET #3	3-66	emo Asses	4-35		
Scheduling Window (Days):	Within 28 days of registration	1 ± 3	22 ± 3	43 ± 3	[64 ± 3	[120 ± 3	Post-Che	2-4 weeks after last dose of chemotherapy ± 3	30 days after last dose (pembro or AVD, ±5 days)	Every 12 weeks

²⁰ Adverse events will be followed for the first 30 days after treatment discontinuation. SAE's will be recorded for 90 days after treatment discontinuation. For patients who undergo allogeneic stem cell transplant (SCT) within 24 months of last study treatment, transplant parameters and adverse events will be recorded according to section 4.6.3 (up to 18 months from the time of SCT).

²¹ Echo or MUGA to be repeated after 4 cycles of doxorubicin

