7.1 Adverse Event Monitoring

Adverse event data collection and reporting, which are required as part of every clinical trial, are done to ensure the safety of subjects enrolled in the studies as well as those who will enroll in future studies using similar agents. Adverse events are reported in a routine manner at scheduled times during a trial (see Section 5 for timepoints). In addition, certain adverse events must be reported in an expedited manner to allow for optimal monitoring and patient safety and care.

All patients experiencing an adverse event, regardless of its relationship to study drug, will be followed until:

- the adverse event resolves or the symptoms or signs that constitute the adverse event return to baseline;
- any abnormal laboratory values have returned to baseline;
- there is a satisfactory explanation other than the study drug for the changes observed; or
- death.

Initial Version date: March 10th, 2017

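### Patients who do not go on to consolidation have no scheduled thyroid panel after the full three-dose pembrolizumab induction; the last one is the pre-dose draw on day 43, after two doses

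*Combined protocol and SAP*

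**What the plan says.** The section 5.0 table has a row for T3, FT4 and TSH. It is marked in three columns: screening, pembrolizumab cycle 3 (day 43 ± 3) and consolidation (cycles 4-35). The AVD, post-chemotherapy, discontinuation and survival follow-up columns are blank. Footnote 12 gives the frequency: "At baseline and every 6 weeks while on therapy with pembrolizumab".

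The CBC and chemistry rows, by contrast, are also marked at AVD 1-2, AVD 3-6 and the discontinuation visit. Footnote 11 lists what the chemistry panel contains, and no thyroid test is on the list.

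Other relevant text:
- Section 4.2.1, on the order of events on a dosing day: "Pembrolizumab should be administered on Day 1 of each 21-day cycle after all procedures/assessments have been completed".
- Section 4.3.1, on immune-related events: "These adverse events may occur shortly after the first dose or several months after the last dose of treatment".
- Section 4.5, on thyroid disorders: "Monitor patients for changes in thyroid function (at the start of treatment, periodically during treatment, and as indicated based on clinical evaluation".
- The off-treatment visit in section 5.0 is timed at "30 days after last dose (pembro or AVD, ±5 days", and footnote 20 adds: "Adverse events will be followed for the first 30 days after treatment discontinuation".
- Section 4.2.3 limits consolidation to selected patients aged 60 or older.

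**The concern.** Safety and tolerability of pembrolizumab with chemotherapy is a secondary objective (section 2.2). Section 8.1.10 lists abnormal thyroid function among events seen in 1 to 10% of patients. For anyone who does not receive consolidation, thyroid testing by schedule stops before the effect of the third dose can be seen, and it stays off throughout chemotherapy, although the protocol itself expects delayed immune events. Mild thyroid dysfunction can be silent, or its symptoms can be put down to chemotherapy. What is at stake is whether such cases are found, treated and counted in the secondary safety summary.

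**Working it through.** **Inputs.** Pembrolizumab cycles are 21 days and AVD cycles 28 days, with AVD given on days 1 and 15 (section 5.0, footnote 1). There are three induction doses (4.2.1). AVD starts 21 days after the third (4.2.2.1). The off-treatment visit is 30 days after the last dose (section 5.0 table).

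**Reproducing the plan's dates.**
- Induction doses: 1 + 21k for k = 0, 1, 2 gives days 1, 22 and 43, as in the table.
- AVD cycle 1: 43 + 21 = day 64, as in the table.
- AVD cycle 3: 64 + 2 × 28 = day 120, as in the table.
- Six-weekly thyroid panels: 1 + 42k gives day 43, the cycle 3 mark, and then day 85.

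**Where the panels fall.** The day 43 panel comes before dose 3, so it follows two doses. Day 85 lies in AVD cycle 1 (days 64 to 91), when the patient is no longer on pembrolizumab and footnote 12 does not apply. Scheduled panels after dose 3 without consolidation: 0.

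**Is the blank row an extraction artefact?** Split into fields, the thyroid row has 13, the same number as the CBC and chemistry rows, and its marks line up with theirs. Footnote 12 says the same as the row. The blanks are the plan's own.

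**Length of the gap.** For c AVD cycles, the last AVD dose falls on day 64 + 28(c − 1) + 14. Adding 30 gives the nominal end of routine adverse event collection; subtracting 43 gives the days since the last scheduled panel.

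| AVD cycles | Last AVD dose (day) | Plus 30 days (day) | Days since day 43 |
|---|---|---|---|
| 1 | 78 | 108 | 65 |
| 2 | 106 | 136 | 93 |
| 3 | 134 | 164 | 121 |
| 4 | 162 | 192 | 149 |
| 5 | 190 | 220 | 177 |
| 6 | 218 | 248 | 205 |

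Four and six cycles are the planned totals after a negative PET#3; the other rows show early stopping or, for five cycles, the discretion allowed for bulky disease. The two-cycle row also applies to one planned path: "Patients age <60 with Deauville score of 4-5 on PET#3 may transition to escBEACOPP". For those patients 93 days counts from the last AVD dose, as the table does. If escBEACOPP counts as study treatment the interval is longer, by an amount the documents do not fix.

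**Scale of the outcome.** Applying 1 to 10% to 30 patients gives 0.3 to 3 patients with any thyroid abnormality. This is only a ceiling for orientation: the exposure behind that range is not stated, and only cases that are new after day 43, silent or mild, and in patients without consolidation would be missed. The documents give no way to estimate that fraction.

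**The case against.** The strongest reply is that the schedule is consistent and tied to exposure: table and footnote agree, and testing follows time on the drug. Much else also remains in place:

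- Section 4.5 asks for periodic and clinically indicated thyroid monitoring during treatment, and AVD is trial treatment.
- Adverse event review and physical examination continue at AVD visits.
- Section 4.6.2 provides a clinic visit at least every three months for up to two years.
- Section 7.3.2 requires reporting of attributed events more than 30 days after the last dose, and section 7.3.6 requires related serious events to be reported at any time.
- Section 7.1 follows patients with a recorded adverse event until, among other endpoints, "any abnormal laboratory values have returned to baseline".

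In addition, the affected patients have finished pembrolizumab, so no dosing decision depends on the result.

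Most of this stands, and it limits the point. It does not remove it. Section 4.5 names no visit after induction. The other safeguards act on symptoms or on events already recognised, and none schedules a test that would find silent dysfunction. Even under an exposure-linked rule, the third dose never gets a scheduled follow-up panel in these patients.

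A reader might also infer that safety tables by age cohort are biased, because only older patients can resume scheduled testing: about 14 × 21 / 42 = 7 or 32 × 21 / 42 = 16 consolidation panels against none. The documents do not support making that a separate criticism. Section 10.3.2 plans descriptive summaries with no test between cohorts, and more testing alongside more pembrolizumab is what exposure-linked monitoring produces.

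**Conclusion.** The gap is real and minor. Patients without consolidation have no scheduled thyroid panel after full induction, and the nominal untested stretch of adverse event collection is 149 days with four AVD cycles and 205 with six, shorter if AVD stops early. These figures assume no delays, a last AVD dose on day 15 of the final cycle, and visits on their nominal dates (windows of 3 and 5 days apply). They measure time without a scheduled test, not harm.

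What can be lost is new-onset silent or mild dysfunction in the secondary safety summary. Two stronger readings do not hold. One is that these patients go without thyroid monitoring altogether; section 4.5 rules that out. The other is that the main conclusions are at risk. The primary endpoint is read from PET#2 and does not depend on thyroid tests. The stopping rule in section 10.3.2 counts toxicities that require discontinuation of pembrolizumab, whereas Table 4.1 continues the drug for grade 2-4 hypothyroidism and grade 2 hyperthyroidism; only grade 3-4 hyperthyroidism may lead to discontinuation, at the physician's discretion.

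**What to change.** In the section 5.0 table and footnote 12, add T3/FT4/TSH for all patients at two existing blood draws: AVD cycle 1 day 1 (day 64, 64 − 43 = 21 days after dose 3) and the 30-day off-treatment visit. The first gives every patient who reaches AVD a panel after the full induction. The second looks for later onset; without it, 192 − 64 = 128 days (four cycles) or 248 − 64 = 184 days (six cycles) would still pass with no scheduled test before routine adverse event collection ends.

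The cost is at most 2 × 30 = 60 extra panels, or 60 × 3 = 180 individual assays, if all 30 patients reach both visits. No visits are added. The analysis plan in section 10.3.2 needs no change.

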6.0 RESPONSE ASSESSMENT

6.1 Measurability of lesions

6.1.1 Measurable disease

Lesions that may be accurately measured in two dimensions by CT, MRI, plain x-ray, or other conventional technique and have a greatest transverse diameter of 1 cm or greater; or palpable lesions with both diameters 2 cm or greater. Splenomegaly alone is not sufficient to qualify as measurable disease. NOTE: PET scans are insufficient for evaluation of measurable disease.

6.1.2 Non-measurable disease

All other lesions including unidimensional lesions, lesions too small to be considered measurable, pleural or pericardial effusion, ascites, bone disease, leptomeningeal disease, lymphangitis, pulmonitis, abdominal masses not confirmed or followed by CT or disease documented only by PET imaging or indirect evidence (e.g., lab values).

6.2 Lymphoma Response Criteria

NOTE: These criteria are based upon the criteria for the LUGANO 2014 Response Criteria (Appendix C). Patients who receive consolidation with pembrolizumab will also have disease assessed by the Immune Response Criteria (Appendix F) as an exploratory assessment.

The criteria use the following categories of response: Complete Response (CR), Partial Response (PR), Stable Disease (SD), Relapse and Progression (PD). In the case of stable disease, follow-up assessments must have met the SD criteria at least once after study entry at a minimum interval of six weeks.

6.3 FDG-PET/CT Guidelines

All patients should have a pre-treatment FDG-PET/CT scan as a baseline to compare with subsequent scans to assess response. This should be performed no more than 35 days (5 weeks) before registration, as is consistent with standard of care.

Investigational FDG-PET/CT (PET #2) will be performed to assess the response to the first three (3) cycles of pembrolizumab lead-in, our primary endpoint,

Subsequent FDG-PET/CT (PET #3) will be completed after the 2nd cycle of AVD.

A fourth FDG-PET/CT (PET#4) will be performed after completion of chemotherapy, prior to starting pembrolizumab consolidation (if applicable), unless patient is Stage I/II and has a negative PET#3; these patients can have a diagnostic CT scan.

Subsequent FDG-PET/CT scans are recommended every 3 months during consolidation until a patient achieves PET-negativity, then only CTs will be obtained. See Section 5-Schedule of Activities for other times of response assessments.

Only full-ring integrated FDG-PET/CT scanners are acceptable (coincidence cameras are not acceptable). The CT of the FDG- PET/CT is used for attenuation correction of PET data and anatomic localization. CT settings and patient preparation should follow institutional guidelines.

42

